5. To analyze the perceived satisfaction rates of the athletes, using the SF-12 questionnaire after the intervention.
6. Know the effective dosage of a specific protocol for the prevention of ACL injuries.

PICO Question

In soccer players with DKV... Does a specific training protocol reduce the risk of ACL injuries compared to the conventional program?

Study hypothesis

A comprehensive and specific 12-week training protocol for the 2023-2024 season will significantly reduce the risk of ACL injuries compared to conventional training for female soccer players with DKV.

METHODOLOGY

Ethical documents and prior registration

This study has the Authorization of the Ethics Committee of the Responsible Research Office of the Miguel Hernández University of Elche for the 2022/2023 academic year and will be registered as a clinical trial in the clinicalTrials platform.

Studio Design

The study is designed as a randomized and controlled, double-blind, unicentric and parallel group clinical trial protocol that will be carried out with the female players of Elche CF and Intercity CF in the province of Alicante. The recommendations of the SPIRIT guide³⁶ have been followed for the realization of this study. Annex I.

Before starting the study, they will be provided with a written informed consent that they must sign to record their intention to participate in it, being able to revoke it at any time and accepting the conditions that will appear in the document (Annex II). They will be randomly assigned to a conventional fitness training program or a specific training protocol for 12 weeks. This study will consist of 3 time measurement points, the first prior to the intervention, the second at the end of the 6-week period of intervention and the last at 4 weeks after its completion. The study schedule and flowchart are in Annex III and IV, respectively.

Participants

The recruited population will be formed by the 44 elite players (22 per team) with a federative record belonging to the first senior team of Elche CF and Intercity CF of the province of Alicante of the national women's football league during the 2023-2024 season, where three weekly training sessions of one hour each are carried out. Prior to the collection of data, permission will be requested from the Club and the coach of both teams to carry out the study at the Martínez Valero Stadium in Elche. In the same way,

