The study will have two physiotherapist evaluators, with at least five years of clinical experience. They will be responsible for the collection and analysis of data, assessments and evaluation of the final results. There will also be two sports physiotherapists, with at least five years of experience in the sports field, who will be responsible for the explanation and supervision of the exercises, in addition to being knowledgeable about the execution of specific training protocols.

A double-blind masking will be carried out, in which the evaluating physiotherapists and the players themselves will be blinded. Sports physiotherapists will be the only professionals who will not be. In addition, interventions and measurements will be performed in separate rooms, which will facilitate the blinding of subjects and evaluators.

Intervention

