First, an invitation will be made to all the players who are part of the teams mentioned above during the 2023-2024 preseason with the aim of starting the intervention during that same season. All respondents will receive a Google survey via WhatsApp. This questionnaire will include questions about the inclusion and exclusion criteria to select the study sample of interest as well as questions about their sports background (position, dominant limb and sports experience); anthropometric measurements (age, height, BMI and weight), which will be provided by the coaches of the selected teams; and aspects related to training (frequency of weekly training and rest period). After completing the survey, three weeks prior to the start of the clinical trial, all players who agree to participate must undergo a final screening to be included in the study. This screening will consist of undergoing a qualitative analysis of the DVJ (Annex VIII), so that, through a simple visual examination, the inclusion of those players who do not present DKV can be ruled out and only those who test positive for DKV can be registered. After selecting the final number of players, a joint talk will be given to both teams to expose the dynamics of the study and the confidentiality of the data. Subsequently, pre-intervention measurements will be carried out by the evaluating physiotherapists to record the initial state of the players. These measures will be: the quantitative analysis of the DVJ, the LESS score, the initial score in the SF-12 scale, the biomechanics of the lower extremities, the muscular activation of the lumbo-pelvic complex and the lower extremity.

During the 12 weeks that the intervention will last, periodic measurements will be made. The last one will take place one month after the end of it. In addition, the players will be asked to refrain from consuming performance stimulants, tobacco or alcohol, non-steroidal anti-inflammatory drugs (NSAIDs) or analgesics 24 hours before each session, as well as strenuous exercise. As a reminder, a WhatsApp will be sent to each athlete the day before each session, indicating the time at which they will be scheduled for training the next day. The appearance of pain during the sessions will not be allowed and, if at any time it appears, the training of the player in question will be stopped immediately and recorded for further analysis.

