The intervention will consist of performing 3 weekly training sessions for 12 weeks to reach a total of 36 sessions of 30-60 minutes each. The days that will be set for training will be Mondays, Wednesdays and Fridays, leaving a rest day between sessions to ensure adequate recovery and quality training. The physical trainers will have to agree so that the training load in both groups is very similar.

Next, we will proceed to detail the intervention that will be carried out in each of the two groups of this clinical trial:

Conventional fitness training group

The players who belong to this group will maintain the usual practice of football training, so no new intervention will be applied.

Training group with a specific ACL injury prevention protocol

This protocol is based on prevention programs that use a multifaceted approach, effective in reducing the risk of ACL injuries compared to those who used only one type of exercise^{14,21,34}. A wide variety of studies defend the importance of working the muscles of the trunk, hip and knee to prevent DKV^{23,28,30}. Therefore, lumbo-pelvic stabilization training (*core* stability) that includes motor stability and strengthening of the gluteal muscles, in addition to strengthening the lower limb itself, will lead to a significant improvement in neuromuscular control of the lower extremities and trunk in addition to producing a significant decrease in DKV and valgus moments^{10,18,20,24,29,30,32}.

The proposed exercise protocol will be designed taking into account the inclusion of three main components. Annex IX:

- Lumbo-pelvic stabilization exercises.
- Lower limb strengthening exercises.
- Integration exercises (plyometrics and balance).

The exercises integrated into the programme will be organised into three phases of implementation:

- **Phase 1** (adaptation - 1st month): Its objective is that the players learn and integrate new patterns while they train.
- **Phase 2** (Proficiency - 2nd month): Aims for players to master new patterns in a controlled environment.
- **Phase 3** (performance - 3rd month): Its objective is to perform exercises in situations as specific as possible and close to the demand and explosiveness of movements typical of the pitch.

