During the execution of all the exercises, verbal and visual inputs will be received, such as the presence of a full-body mirror so that they can correct positions and verbal indications focused on lumbo-pelvic stability and the biomechanics of the lower limb to improve the concentration and motivation of the players during the execution of the scheduled exercises^{9, 12,17,21,33}.

The progression of the exercises will be established by increasing the speed of execution of the same, increasing the complexity of the task to be performed and by promoting neurocognitive implications (for example, counting backwards from 10 to 0 during the execution of the exercises). In addition, compliance with the proposed protocol will be verified through weekly self-reported questionnaires that will be sent via WhatsApp and will be part of the records to be analyzed later by the evaluators.

Expected results

The results we expect to obtain from the intervention group are directly related to the modification of risk factors such as DKV and the decrease in the injury incidence of ACL. It is expected to improve proprioception, body balance and motor control, not only of the lower extremities, but of the entire lumbo-pelvic complex. In addition, it is expected to improve sports performance and ball control on the pitch.

All changes that occur between the players in the intervention group will be measured and recorded. Changes in the neuromuscular control of the knee and the mechanical behavior of the joints proximal and distal to it^{23,28} will be analyzed with a jump-landing test (DVJ)^{19,27,28,32}. Taking advantage of the

previous test, the biomechanics of the jump landing will be evaluated and the risk of non-contact injuries will be identified using the LESS scoring system. In addition, during the execution of the DVJ, the data obtained from the activation of the different pre- and post-intervention muscle groups will be collected and processed with an EMG system^{19,27,29,30}. All these positive changes would imply a lower incidence of injury for the players in the intervention group, as well as higher levels of satisfaction compared to the control group.

Statistical analysis

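### The trial is labelled double-blind with blinded players, but players will know which training they do, so the SF-12 comparison is unblinded; evaluator blinding is achievable but weakly protected.

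*Combined protocol and SAP*

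**What the plan says.** The Studio Design section describes a "randomized and controlled, double-blind, unicentric and parallel group clinical trial protocol". Randomization and blinding says that "the evaluating physiotherapists and the players themselves will be blinded", and of the sports physiotherapists, "Sports physiotherapists will be the only professionals who will not be". The only mechanism offered is that "interventions and measurements will be performed in separate rooms, which will facilitate the blinding of subjects and evaluators".

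The arms are described under Intervention. Control players "will maintain the usual practice of football training, so no new intervention will be applied". The other arm follows a three-phase programme. Of the first phase the protocol says: "Its objective is that the players learn and integrate new patterns while they train". All its exercises are done with verbal and visual input, including "the presence of a full-body mirror so that they can correct positions".

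Four further statements bear on the point:

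- Randomization and blinding allocates teams by coin toss, and makes the two evaluating physiotherapists responsible for collecting and analysing the data.
- The description of the specific protocol sends weekly self-reported compliance questionnaires to those evaluators for later analysis.
- The SF-12 is specific objective 5 and is taken before and after the intervention. Expected results predicts greater satisfaction in the intervention arm than in the control arm.
- Limitations does not mention that players are unblinded.

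**The concern.** Blinding of players is stated as a property of the design, but the description of the arms is incompatible with it. Separate rooms may keep an evaluator from seeing the training. They cannot hide from a player what she herself is doing.

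Two things are at stake. First, the SF-12 is answered by the player, and the protocol predicts a difference in a stated direction. When one arm receives something new and the other does not, knowledge of the training can contribute to such a difference. A report using the double-blind label would imply protection against this that the trial does not have. Second, evaluator blinding is the protection that the drop vertical jump (DVJ) and Landing Error Scoring System (LESS) assessments need, and the plan gives it no procedure beyond separate rooms.

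**Working it through.** **1. Player blinding: the statements side by side.**

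| Question | What the protocol says | Section |
|---|---|---|
| Are players blinded? | Yes | Randomization and blinding |
| What do controls receive? | Usual training, nothing new | Conventional fitness training group |
| What does the other arm receive? | A new three-phase programme with mirror and verbal cues | Training group with a specific ACL injury prevention protocol |
| Is there a sham or attention control? | None described | – |
| How is blinding achieved? | Separate rooms | Randomization and blinding |

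For a player to be blinded, she would have to be unable to tell usual training from the new programme. Nothing described would prevent her from telling them apart. The first row therefore cannot hold together with the second and third.

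**2. Evaluator blinding.** This is stated separately and is feasible. There are two routes by which it can fail:

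- Teams are the unit of assignment, so learning the arm of one player reveals the arm of all her teammates.
- Questionnaires on compliance with the protocol form part of the records that the evaluators analyse.

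The Strengths section says that the two evaluators will not know the results of the other measurements. That limits the influence of one result on another. It does not conceal the arm.

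**3. The plan's own figure.** The sample size section uses a standardised difference of 1, alpha 0.05 (two-sided according to Statistical analysis) and 90% power. Per arm, n = 2 × (1.960 + 1.282)² / 1² = 21.0, rounded up to 22, or 44 in total. This agrees with the plan, and nothing in this point changes it.

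**4. Illustration only.** The documents give no size for reporting bias. Assume no true SF-12 effect, a pure reporting shift of b SD, and independent players. The t statistic then has noncentrality b × √(n/2). The probability of a significant result at two-sided 0.05 is:

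| Assumed shift b | Noncentrality (22 per arm) | 22 per arm | 24 per arm |
|---|---|---|---|
| 0.1 SD | 0.33 | 6.2% | 6.3% |
| 0.2 SD | 0.66 | 9.9% | 10.4% |
| 0.3 SD | 0.99 | 16.3% | 17.4% |
| 0.4 SD | 1.33 | 25.4% | 27.4% |

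**5. Why these are not error rates for this trial.** With one team per arm, players are not independent. If the intra-team correlation is ρ and there are m = 22 players per team, the true variance of the mean difference exceeds the variance that the t-test assumes by a factor of 1 + mρ/(1 − ρ). With no reporting bias at all:

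| Assumed ρ | Variance factor | Effective cut-off (2.018/√factor) | False-positive rate |
|---|---|---|---|
| 0.02 | 1.45 | 1.68 | about 10% |
| 0.05 | 2.16 | 1.37 | about 18% |
| 0.10 | 3.44 | 1.09 | about 28% |

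The documents do not give ρ either. The 5% starting point for the table in step 4 therefore does not hold in this design.

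**The case against.** The strongest reply is that unblinded participants are normal in exercise trials, that evaluators are blinded, and that most measures (motion capture, EMG, force platform) do not depend on what a player reports. This limits the reach of the point but does not answer it. The fault is in claiming player blinding, and no text resolves the contradiction.

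Several stronger readings are tempting, and the objection to each stands:

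- **That the trial has no effective blinding.** The documents do not support this. Evaluator blinding is claimed separately, and separate rooms help with it.
- **That the joint talk tells players their arm.** It is described only as "a joint talk will be given to both teams to expose the dynamics of the study and the confidentiality of the data". The text does not say that allocation or hypothesis is disclosed, or whether the talk comes before the coin toss. Players will know what training they do. Whether they know which programme is expected to do better is not shown.
- **That the 36 sessions mark out the intervention arm.** That count, and the request for similar training load in both groups, come before the text turns to each group, and the teams already train three times a week. The count may be common to both arms. The argument rests on content, mirror and cues.
- **That the SF-12 false-positive rate rises from 5% to somewhere between 10% and 25%.** This needs an assumed shift of 0.2 to 0.4 SD and independent players. The documents supply neither.

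One caution applies to the point about club revealing arm. Studio Design speaks of participants being randomly assigned, whereas Randomization and blinding assigns teams. That point relies on the second statement. The point about player blinding holds under either.

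**Conclusion.** The claim that players are blinded is wrong as written, and the SF-12 comparison is unblinded. This follows from the protocol's own description of the arms and needs no numerical assumption.

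The size of any resulting bias cannot be derived from the documents. It depends on how far knowing one's training shifts SF-12 answers, and the plan gives no figure for that.

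Evaluator blinding is achievable but under-protected, assuming that allocation is by team and that the compliance questionnaires are handled as described.

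A reader might infer that the main result is compromised. The documents do not support that: the main objective is prevention of ACL injury, and the SF-12 serves one of six specific objectives. The point should be corrected before the trial is reported, but it does not by itself invalidate the main comparison.

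**What to change.** 1. In Studio Design and in Randomization and blinding, replace double-blind with assessor-blind, and delete the statement that players are blinded.
2. Add the absence of player blinding to Limitations.
3. State that the SF-12 is an unblinded self-reported outcome and will not on its own support a claim of benefit.
4. Withhold compliance questionnaires and club identity from the evaluators until DVJ and LESS scoring is complete.
5. Tell players not to mention club or programme to the evaluators.
6. Where jumps are recorded, give the files codes and score them in random order, mixed across clubs and visits. The protocol does not say that recordings are kept, so this step is conditional.

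The cost is a less impressive design label, a weaker SF-12 claim and minor file handling, with someone other than the evaluators holding the compliance records in the meantime. No sample size or test changes. Because the same two evaluators may see players at repeated visits, these steps reduce the risk of unblinding but do not remove it.

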the recruitment will be carried out through a direct contact, as an interview, with the coach, the physiotherapist and the physical trainer of the participating teams.

Inclusion and exclusion criteria

The inclusion criteria will be:

- Football players registered and federated in the corresponding team.
- With an age range between 18 and 35 years.
- Minimum experience of one year playing football.
- With the presence of DKV.

The exclusion criteria will be:

- Previously injured subjects of ACL or other knee ligament injury.
- Subjects with a history of lower extremity injuries that have resulted in surgery during the six months prior to the study.
- Players with chronic illnesses that may affect test results.
- Subjects who practice other sports in the professional field.

Study variables and measurements

To record the number of injuries produced among the players of both groups at the end of the study and the frequency of weekly training, an Excel table will be used. The kinetics and kinematics of the lower extremities will also be analyzed with a motion capture system, surface EMG markers and a force platform. The LESS scoring system (Annex V) and the DVJ task will be used to identify the risk of injury during the jump-landing task and the presence of DKV among the players, respectively. In addition, we will measure their pre- and post-intervention satisfaction rates using the SF-12 questionnaire³⁸. Annex VI.

Sample size

An analysis was performed with Epidat 4.2 software to calculate the sample size required in the present study. A comparison of independent means will be performed and a standardized mean difference of 1, a significance level of 0.05, a 95% CI and a power of 90% will be considered, which determines a total sample size of 44 subjects, 22 in each group. It is necessary to consider an abandonment rate, so we will increase the sample by 10%. Therefore, the total sample size will be 48 women, 24 in each study group. Annex VII.

Randomization and blinding

Teams will be randomly assigned to one of the two groups in a simple manner and will be performed once subject selection has been completed. This assignment will be hidden and will be carried out by a person independent of the study. The randomization method will consist of the toss of a coin assigning "heads" to the intervention group and "tails" to the control group.

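### Compliance records that appear to exist for the intervention arm only are to be analysed by the evaluators who are meant to be blinded and who also assess and analyse the outcomes

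*Combined protocol and SAP*

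**What the plan says.** Under Randomization and blinding, the protocol states that "the evaluating physiotherapists and the players themselves will be blinded". Of the sports physiotherapists, who teach and supervise the exercises, it says "Sports physiotherapists will be the only professionals who will not be". The same section describes the two evaluators' tasks: "They will be responsible for the collection and analysis of data, assessments and evaluation of the final results". On allocation it says "Teams will be randomly assigned to one of the two groups in a simple manner", by the toss of a coin.

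Under Intervention, in the part on the specific ACL prevention arm, it says that "compliance with the proposed protocol will be verified through weekly self-reported questionnaires that will be sent via WhatsApp" and that these questionnaires "will be part of the records to be analyzed later by the evaluators". That part introduces its content with "The proposed exercise protocol will be designed taking into account the inclusion of three main components". Players in the conventional arm "will maintain the usual practice of football training, so no new intervention will be applied".

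**The concern.** A record of how well a player followed the specific protocol is informative about her arm if only one arm has a protocol to follow. The plan passes such records to the people whose blinding it relies on. Two things are at stake.

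- **Analysis.** The evaluators also analyse the outcomes. The Statistical analysis section leaves them choices: median with interquartile range or mean with standard deviation, and ANOVA or Mann-Whitney after a normality check. Such choices are best made without knowing which group is which.
- **Scoring.** LESS is scored by a rater. If the evaluators see a compliance record before a later visit is scored, expectation can enter the score.

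**Working it through.** No figure in the plan is attached to this point, so the check sets the sections side by side.

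1. **Who the evaluators are.** Randomization and blinding names two evaluating physiotherapists. No other group in the document carries that title, so the evaluators in the compliance sentence are read as the same two people.

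2. **What they are given.** The compliance sentence concerns the proposed protocol and stands in the section on the intervention arm. The description of the conventional arm gives it no new intervention. A control player would have nothing to report on such a form, and no matching control form is described. One-arm records are therefore a reasonable inference, not stated text.

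3. **How far one record reaches.** There are two teams, and each team goes to one arm. Once the arm of one player whose team is known is revealed, her team's arm is known, and the other team must be in the other arm. That covers all players: 2 × 22 = 44 under Participants, or 2 × 24 = 48 under Sample size.

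4. **Whether scoring can be affected.** Studio Design gives three measurement points: before the intervention, at 6 weeks, and 4 weeks after completion. The Intervention section mentions periodic measurements during the 12 weeks and a last one a month after the end. If the questionnaires run weekly from the start of training, every measurement except the first falls after they begin. On the three-point schedule that is 3 − 1 = 2 of 3 visits. Whether the evaluators have read any form by then depends on what *later* means, and the text sets no date or event for it.

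5. **What safeguards are stated.** Interventions and measurements take place in separate rooms, which does not mask a written record. Under Strengths, the two evaluators do not know the results of the other measurements, which does not conceal allocation. The text describes no coded arm labels, no separate data handler and no hold on these records. The annexes it cites are not part of the text reviewed.

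6. **Result.** Steps 1 to 3 put the evaluators' role as blinded analysts in conflict with their role as analysts of compliance. Steps 4 and 5 leave earlier exposure, during scoring, possible but not established.

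**The case against.** The strongest reply is about timing. *Later* can well mean after the last visit. In that case no LESS score is affected. The text also does not say to whom the players return the questionnaires, so a reader who infers that the forms reach the evaluators every week, and that following the plan necessarily unblinds the scoring, goes further than the wording allows. This stands: contaminated scoring is a possibility the text leaves open. It does not remove the analysis problem, because the same two people analyse the outcomes whenever they read the forms, and nothing puts the outcome analysis first.

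Second, one-arm forms are inferred. The plan also records weekly training frequency for both groups and wants similar training load, so some neutral log for controls is conceivable. This stands as a caveat, but no such form is described.

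Third, a reader might try to turn an assumed rater shift into an inflated false-positive rate. The documents do not support that. They give no shift. The usual 5% reference for a comparison of independent players also does not apply with one team per arm, unless the between-team correlation is zero. Any such figure would restate its own assumption and mix this leak with the separate problem of team allocation.

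Fourth, the reach is limited. Rater expectation chiefly threatens LESS. The outcome DVJ is described as quantitative, and motion capture, EMG and a force platform depend less on judgement. The main objective is prevention of ACL injury, and LESS is not named as primary. This stands.

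Last, blinding is fragile under team allocation whatever is done here. That is true, but it does not justify keeping a leak that the protocol itself writes in.

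**Conclusion.** The point holds in a limited form. As written, the outcome analysis is done by people who can know the arms, which contradicts the statement that only the sports physiotherapists are unblinded. Rater-scored outcomes, chiefly LESS, could also be scored with knowledge of the arm, because access to the records is not tied to the last visit.

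This rests on two assumptions: that compliance records exist for the intervention arm only, and that the evaluators know the team of at least one player who returned one. Given both, one record is enough to reveal every player's arm. The size of any resulting bias cannot be derived from the documents, and none is claimed. The correction is cheap and should be made.

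**What to change.** **Compliance paragraph of the specific-protocol arm.** State that the sports physiotherapists, who are already unblinded, hold and summarise the returned questionnaires. State that the evaluators see no compliance or session record until both conditions are met: all outcome scores, including the last visit, are locked, and the outcome analysis has been run.

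**Randomization and blinding, and Statistical analysis.** State that outcomes are analysed under arm codes A and B, with team names removed from the analysis file, and that the code is opened only after that analysis has been run. Compliance is analysed after the code is opened.

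The order matters. Releasing the records at score lock alone would not be enough: the evaluators are also the analysts, and one record could break the A/B code before the analysis is run.

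**Cost.** A few sentences of wording and a named holder for the forms, with no extra staff and no change to the intervention or the sample size. Compliance results come later. Self-reports returned to the physiotherapists who supervise the exercises may be somewhat more favourable than reports to someone else, and this should be acknowledged when compliance is reported. The change removes one leak; it does not by itself secure blinding when whole teams are allocated.
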